Lumbar Puncture and Syphilis Outcome

ID: STUDY00001718

16 Dec 2020

Participants were enrolled from September 2013 to March 2018. Study enrollment criteria changed over its course because of slow accrual. The original plan was to enroll PLWH with a new syphilis diagnosis who had serum RPR titer ≥ 1:32 or peripheral blood CD4+ T cells ≤ 350/ul who did not meet CDC criteria for lumbar puncture based on symptoms [5] and to randomize them to LP vs. no LP. Of note, although CDC criteria for lumbar puncture include cognitive dysfunction, we did not consider cognitive complaints as a reason to exclude study participants because cognition was the focus of our study. After the first year only 32 randomized individuals were entered, and the study was opened to persons not infected with HIV and to individuals who declined randomization. The latter 186 individuals were not restricted by serum RPR titer, peripheral blood CD4 or symptoms, with a plan to match eligible individuals to the eligibility criteria for the original study. We systematically collected the reason for not agreeing to randomization in 167 participants. The most common was that the provider recommended LP (n=132). Individuals who were randomized were not allowed to re-enroll in the study with a new episode of syphilis, but those who were not randomized could re-enter and could be randomized or not with a subsequent episode of syphilis.

The first randomized visit for individuals who were ever randomized, and the first nonrandomized visit for those who were never randomized could be included in the analysis if the participant completed the CogState battery. All randomized participants were included in the analysis; 2 individuals were randomized after a previous, nonrandomized syphilis episode, 6 and 8 months later. Of the 186 nonrandomized participants, analysis was restricted to those with serum RPR titer ≥ 1:32 or, for PLWH, peripheral blood CD4+ T cells ≤ 350/ul. All

nonrandomized participants endorsed normal vision, no photophobia or gait abnormality, and normal or at most mild hearing loss based on our previous observation that these symptoms predicted a reactive CSF-VDRL [8]. Ninety-six individuals were included in the entry analysis (Figure 1).

Procedures

Participants underwent a medical history, neurologic examination, blood draw, urine toxicology screen, and lumbar puncture, when indicated. The participant's provider and the participant decided whether neurosyphilis treatment was indicated based on CSF abnormalities alone; neither were aware of cognitive assessment results.

Neuropsychological assessment

The neuropsychological assessment included the Wide Range Achievement Test-third edition (WRAT-3) reading subtest [9] as an assessment of premorbid verbal intelligence, a revised version of the Lawton and Brody instrumental activities of daily living (IADL) scale [10, 11] and the Medication Management Test-Revised (MMT-R) [10, 12], the Beck Depression Inventory (BDI-II) [13], and the CogState battery [14]. The CogState consists of computerized neuropsychological tests and has been used in clinical and research settings, including in PLWH [15-18]. It includes seven tests spanning cognitive domains of psychomotor function, attention, working memory, executive function, and verbal learning. To assess subjective cognitive impairment, we used question 19 on the IADL (difficulties due to primary cognitive problems or

to cognitive and physical problems) and question 19 on the BDI-II (difficulty with concentration). Participants were asked to return at 24 and 52 weeks for follow-up IADL, MMT-R and CogState battery.

Laboratory Methods

Cerebrospinal fluid white blood cell (WBC) enumeration and CSF-VDRL reactivity were determined in a Clinical Laboratory Improvement Amendments (CLIA)-certified hospital clinical laboratory. HIV RNA and peripheral blood CD4+ T lymphocyte concentrations were obtained by medical record review. Serum RPR titers were performed in a research laboratory [19]. Detection of *Treponema pallidum* subspecies *pallidum* (*T. pallidum*) DNA in blood was determined as previously described [20, 21]. Only samples collected within 8 days of treatment of the current episode of syphilis were tested based on our experience that *T. pallidum* DNA is rarely detected in blood samples after this time (unpublished data).

Data analysis

Assessment of cognitive impairment was based on age adjusted normative data from CogState and was categorized as none (all test scores > -1 standard deviation [SD] of normative data), mild impairment (two test scores < -1 SD, or one test score < -2 SD), moderate impairment (two test scores < -2 SD) or severe impairment (three test scores < -2 SD). For the entry analysis, the latter two categories were combined. For the follow-up analysis, participants were categorized as improved if they had any impairment at study entry and improved by at least one category, or as

normalized if they improved to no impairment. Participants were categorized as declined if they were not severely impaired at entry and declined by at least one category.

For this study, we defined abnormal CSF as WBCs >5/ul. Because we included persons not infected with HIV and because our PLWH were largely on antiretrovirals with suppressed plasma HIV RNA, we were unlikely to overdiagnose neurosyphilis.

WRAT scores were normalized based on age [9]. Years of education was categorized as 9-12 vs. ≥13 years (high school or less vs. more than high school), BDI- II was categorized as 0-13 (none or mild depression) vs. ≥14 (moderate or greater depression), MMT-R was categorized as <5 vs. ≥5 [10, 22], and IADL was categorized as dependent vs. independent.

Descriptive statistics are expressed as number (percent) or median (interquartile range [IQR] or 95% confidence intervals). Proportions were compared by the Chi-square or Fisher's exact test, and comparisons of continuous variables by Mann-Whitney U test. Odds ratios (ORs) with 95% CI for categories of cognitive impairment at study entry were determined by univariate or multivariate ordinal logistic regression. Time to cognitive change was assessed by log rank test, and hazard ratios were determined by Cox regression. P-values <0.05 were considered statistically significant.

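### Some participants were randomized to LP or no LP, but the Data analysis section specifies no comparison by assigned arm, so the plan as written does not call for an estimate of the randomized contrast

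*Combined protocol and SAP*

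**What the plan says.** The opening section, on enrollment, says that the original plan was to take people living with HIV and new syphilis who met serum RPR or CD4 criteria and "to randomize them to LP vs. no LP". Accrual was slow: "After the first year only 32 randomized individuals were entered". The study was then opened to people without HIV and to people who declined randomization, of whom 186 entered. A reason for declining was collected from 167 of them, and for 132 it was that their provider advised LP.

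On who is analysed, the same section says "All randomized participants were included in the analysis". It adds that "2 individuals were randomized after a previous, nonrandomized syphilis episode, 6 and 8 months later". For the others it says "Of the 186 nonrandomized participants, analysis was restricted to those with serum RPR titer" of 1:32 or more or, in people living with HIV, a CD4 count of 350/ul or less. It also reports that none of the nonrandomized participants had visual, photophobic or gait complaints, or more than mild hearing loss. The entry analysis has 96 people.

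Under Procedures, treatment was not randomized: provider and participant "decided whether neurosyphilis treatment was indicated based on CSF abnormalities alone; neither were aware of cognitive assessment results".

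Under Neuropsychological assessment, follow-up testing is at 24 and 52 weeks. The Data analysis section defines improvement (with normalization as its fullest form) for people impaired at entry, and decline for people not severely impaired at entry. It then names the methods: Chi-square or Fisher's exact test, Mann-Whitney U, ordinal logistic regression for impairment category at entry, a log-rank test for time to cognitive change, and Cox regression for hazard ratios.

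**The concern.** A log-rank test compares groups and a Cox hazard ratio belongs to a covariate, yet the section names neither. Nowhere does it mention LP versus no LP, assigned arm or randomized status as a group, covariate or stratum. The only regression tied to a time point concerns impairment at entry, which allocation to LP cannot change.

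At stake is the question in the study's title, whether LP affects outcome. Comparison by assigned arm is the only answer that does not depend on why a person had an LP. Every other contrast the text could support is observational. CSF findings exist only for people who had an LP. Treatment followed the CSF result. LP outside the randomized group could reflect the provider's judgement. Unawareness of the cognitive results limits selection on measured cognition, but not on other grounds.

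**Working it through.** The plan states no sample size, power, effect size or event count, so it has no figure to reproduce. The check is mainly a reading of each analysis statement, with some arithmetic on the counts.

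**1. Analysis statements, one by one.**

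| Method in the Data analysis section | Outcome named | Groups or covariates named | Assigned arm named |
|---|---|---|---|
| Chi-square or Fisher's exact | proportions, in general | none | no |
| Mann-Whitney U | continuous variables, in general | none | no |
| Ordinal logistic regression | impairment category at entry | none | no |
| Log-rank test | time to cognitive change | none | no |
| Cox regression | hazard ratio | none | no |

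The opening section sets out who may be analysed and which visit counts as entry. It does not define a randomized-only set.

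**2. How many were randomized.** I read the 32 as the number randomized by the end of the first year. Nonrandomized entry opened only after that. The two people randomized 6 and 8 months after a nonrandomized episode must therefore be additional: 32 + 2 = 34 at least. If all randomized participants are among the 96 in the entry analysis, 96 is the ceiling. The text gives neither the final total nor the arm sizes.

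**3. What the nonrandomized counts describe.** 132/167 = 79% gave provider advice as the reason for declining. With at least 34 of the 96 randomized, the nonrandomized part of the entry analysis is at most 96 − 34 = 62, and 62/186 = 33%. At least two thirds of the 186 are therefore outside the analysed set, and the 79% cannot be carried over to those inside it.

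**4. Precision of the randomized contrast.** Assuming 1:1 allocation, SE(log HR) ≈ 2/√events, and the 95% interval extends by a factor of exp(1.96 × SE) either way. Assume, for improvement, that between 30% and 70% are impaired at entry, that the same range of those improve, and that nobody is lost.

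- Low end: 34 × 0.3 × 0.3 = 3.06 events; SE = 2/√3.06 = 1.14; factor exp(2.24) = 9.4.
- High end: 96 × 0.7 × 0.7 = 47.0 events; SE = 2/√47.0 = 0.292; factor exp(0.572) = 1.8.

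The rates and the allocation are assumptions, and the formula is poor at about 3 events. The range shows only that the text does not fix the precision, and that much of it is wide.

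**The case against.** The strongest reply is that this is a short methods text in the past tense, and that its silence is general. No test in it has named groups, so silence about arm does not show that the arm comparison was left out. That is fair as far as it goes. A reader might infer that the comparison was never made, or that randomization was abandoned; the documents support neither. They say that the study was opened to people who declined, not that randomization stopped. What stands is narrower: the written plan does not ask for the estimate. Figure 1 is not shown, but it is cited for the count in the entry analysis, and nothing in the text suggests that it defines comparison groups.

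A reader might also infer that follow-up change was compared by LP in a pooled set, so that randomized and provider-chosen LP could not be separated. The text describes no such comparison. Randomized and nonrandomized visits are distinguished, so the groups can be separated. Nor does the 79% show who underwent LP or who was analysed: it is a reason for declining, recorded before restriction. The RPR, CD4 and symptom criteria further narrow the grounds on which providers might have selected people, although they do not replace randomization.

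Finally, the randomized comparison may be too small to be decisive, and an analysis added now may be post hoc. Both points have weight. They are reasons to report an estimate with its interval and to state when it was specified, not to leave it out.

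**Conclusion.** The point holds in a limited form and should be fixed. Some participants, at least 34, were randomized to LP or no LP, and all of them were analysed together with a restricted nonrandomized group. The Data analysis section specifies no comparison by assigned arm and no randomized-only set. The plan as written therefore does not call for an estimate of the contrast that the study randomized to obtain.

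Unnamed log-rank and Cox groups alone would be a matter of missing detail. The absence of the assigned-arm comparison gives the point its weight.

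It does not extend to the entry odds ratios, which this gap leaves untouched, and it is not a finding that any reported result is biased. The minimum of 34 rests on reading the 32 as the first-year total. No precision is claimed, because the text gives neither the final number randomized nor the number of events.

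**What to change.** - Add an intention-to-treat comparison of LP with no LP by assigned arm, in randomized participants only, with the first randomized visit as entry, as the opening section already provides.
- Make it separately for improvement (those with any impairment at entry) and for decline (those not severely impaired at entry), since the two outcomes have different risk sets.
- Report arm sizes, numbers at risk for each outcome, numbers assessed at 24 and 52 weeks, and a 95% confidence interval. Present the result as an estimate, not a test. Adjustment for entry cognitive category is optional and depends on the number of events.
- State when the comparison was specified: the document is dated December 2020 and enrollment ended in March 2018.
- Name the groups or covariates in the log-rank and Cox analyses.
- Report any LP contrast in nonrandomized participants separately. Label it, and all CSF and treatment contrasts, as observational.

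The cost is some wording and two analyses of data in hand, with no change to study conduct. The drawback is an imprecise estimate that loss to follow-up may affect, so the numbers assessed at each visit matter as much as the hazard ratio.

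### Does the either/or eligibility rule (RPR ≥ 1:32, or low CD4 in PLWH) invalidate the entry odds ratios because no adjustment set is named?

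*Combined protocol and SAP*

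**What the plan says.** The opening section (before Procedures) builds the analysis set from two streams.

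- **Nonrandomized participants:** "analysis was restricted to those with serum RPR titer ≥ 1:32 or, for PLWH, peripheral blood CD4+ T cells ≤ 350/ul".
- **Randomized participants:** the original plan took PLWH who "had serum RPR titer ≥ 1:32 or peripheral blood CD4+ T cells ≤ 350/ul". "After the first year only 32 randomized individuals were entered", and then "the study was opened to persons not infected with HIV and to individuals who declined randomization". No RPR rule is stated for HIV-uninfected people who were randomized. "All randomized participants were included in the analysis".

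"Ninety-six individuals were included in the entry analysis".

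On the model, the Data analysis section says: "Odds ratios (ORs) with 95% CI for categories of cognitive impairment at study entry were determined by univariate or multivariate ordinal logistic regression". It gives cut-points for education, BDI-II, MMT-R and IADL but attaches none of them to a model. It gives no cut-point for RPR and does not list RPR, CD4 or HIV status as a predictor.

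**The concern.** A rule that admits people through either of two routes links the two routing variables among those admitted, even if they were unrelated beforehand. Here the link is extreme. Under the quoted rule and the original PLWH criteria, the low-RPR group consists entirely of PLWH with CD4 ≤ 350, while the high-RPR group mixes HIV-uninfected people with PLWH at any CD4. If low CD4 or HIV itself affects cognition, an unadjusted comparison of high with low RPR partly compares HIV/CD4 strata.

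RPR, CD4 and HIV status define the population and are recorded, so relating them to entry impairment would be a natural step. The plan permits an unadjusted odds ratio, tests at 0.05 and commits to no adjustment set. A real RPR association could then be hidden, or a spurious one reported.

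**Working it through.** The documents give no RPR odds ratio, effect size or power statement, so there is no figure to reproduce.

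**1. What follows from the text alone.** Under the stated rules, RPR < 1:32 implies PLWH with CD4 ≤ 350. The only possible exception is HIV-uninfected randomized participants. At least 32 of the 96 were randomized in the first year, when only PLWH were eligible. If the original criteria continued for PLWH, the exception is therefore at most 96 − 32 = 64. The actual number is not in the available text; Figure 1, which is not reproduced there, may show it.

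**2. One worked case.** Every input here is an assumption: 80% HIV-infected, 30% of PLWH with CD4 ≤ 350, 60% with RPR ≥ 1:32, all independent; reference risk 50% for any impairment and 20% for moderate or severe; low-CD4 odds ratio (OR) 2, no HIV effect, no RPR effect; no HIV-uninfected person with low RPR included.

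- Share with low RPR: (0.8 × 0.3 × 0.4) / (0.6 + 0.096) = 0.138, about 13 of 96.
- Low-CD4 share: 100% of the low-RPR group; 0.8 × 0.3 = 24% of the high-RPR group.
- Any impairment: low RPR, odds 2. High RPR, risk 0.76 × 0.5 + 0.24 × 0.667 = 0.54, odds 1.174. Crude OR 1.174 / 2 = 0.59.
- Moderate or severe: low RPR, odds 0.5. High RPR, risk 0.76 × 0.2 + 0.24 × 0.333 = 0.232, odds 0.302. Crude OR 0.302 / 0.5 = 0.60.

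The proportional-odds fit across both thresholds gives 0.595, where the truth is 1.

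**3. Range.** Large-sample proportional-odds fits, RPR dichotomized at 1:32. Assumed grid: 60 or 80% HIV-infected, 20 or 40% of PLWH with low CD4, 50 or 70% with high RPR, reference risks 40/15, 50/20 or 60/30%. Columns show the share of HIV-uninfected people with RPR < 1:32 who were admitted.

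| Assumed effects | 0% | 25% | 50% | 100% |
|---|---|---|---|---|
| Low-CD4 OR 2, RPR null | 0.54–0.63 | 0.66–0.75 | 0.73–0.84 | 0.82–0.93 |
| Low-CD4 OR 2, true RPR OR 2 | 1.08–1.25 | 1.31–1.48 | 1.44–1.67 | 1.61–1.84 |
| HIV OR 2 only, RPR null | 0.76–0.88 | 0.93–1.04 | 1.03–1.17 | 1.13–1.29 |
| Low-CD4 OR 2 and HIV OR 2, RPR null | 0.41–0.56 | 0.66–0.79 | 0.76–1.00 | 0.92–1.20 |
| No CD4 or HIV effect, RPR null | 1.00 | 1.00 | 1.00 | 1.00 |

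The direction is not fixed. It is downward if low CD4 worsens cognition and either HIV has no separate effect or no HIV-uninfected person with low RPR was included; otherwise it can go either way. A reversal needs particular inputs: a true RPR OR of 1.5 with low-CD4 OR 2 appears as 0.81–0.94 at 0% admitted.

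**4. Coding.** The large figures need a split at 1:32, which the Data analysis section does not specify for RPR. With log2 titer (assumed SD 2 doublings), low-CD4 OR 2 and null RPR, the crude OR per doubling is 0.92–0.96 / 0.94–0.98 / 0.96–0.99 at 0 / 50 / 100% admitted.

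**5. At n = 96** (simulation, reference risks 50/20%, low-CD4 OR 2). With dichotomized RPR and no true effect, a nominal 5% test of the crude OR rejects in 8–20% / 6–13% / 4–7% of samples at 0 / 50 / 100% admitted, against 3–6% for a model that also contains HIV/CD4 status. For a true RPR OR of 2, that joint model has power of 8–24% / 16–34% / 19–33%.

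**The case for a change.** The strongest case for a change is that permission is not commitment. The plan allows the adjusted model but does not require it, and the variables most exposed to the selection rule are the ones an investigator would want to examine. The remedy costs a few sentences and one model on data already collected. The gain would be validity: for a true RPR OR of 2, interval coverage is 93–97% with the joint model against 77–92% with the crude one at 0% admitted.

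The selection logic stands, and so does the advice on interpretation. What does not stand is the step to a defect. Four conditions must all hold: RPR is analyzed; it is analyzed only crudely; a conclusion is drawn from that; and HIV or CD4 affects cognition. The documents state none of them. A crude odds ratio is also a valid description of these 96 people; it misleads only if read as the RPR association at a given HIV/CD4 status. The joint model recovers the true value in these calculations because the data were generated under that same model, so its advantage in real data is less certain.

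**Conclusion.** No change to the plan is needed. The eligibility rule does tie low RPR to PLWH with low CD4, and that part rests on the text alone. The size and even the direction of any distortion rest on assumed prevalences, effect sizes and RPR coding: from 0.54–0.63 for a null effect in the downward case worked above, through modest departures with log2 titer, to none if neither CD4 nor HIV matters. No stated analysis is shown to give a wrong result. The remaining gap is an unnamed list of predictors and covariates, and the permitted adjusted ordinal model lets an analyst fill it sensibly.

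If RPR is related to entry impairment, the sensible reading comes from a model that also contains HIV/CD4 status in three levels (HIV-uninfected; PLWH with CD4 > 350; PLWH with CD4 ≤ 350), with crude odds ratios treated as descriptive. Intervals will be wider, a dichotomized RPR estimate will rest largely on low-CD4 PLWH, and at the power shown a null result would say little. "Participants were enrolled from September 2013 to March 2018", so only analysis and interpretation are open in any case.

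### Does defining abnormal CSF by white cell count alone, when CSF-VDRL was also measured, call for a change to the analysis?

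*Combined protocol and SAP*

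**What the plan says.** Under Laboratory Methods both markers are recorded: "Cerebrospinal fluid white blood cell (WBC) enumeration and CSF-VDRL reactivity were determined" in the hospital laboratory. Under Data analysis only one enters the definition: "For this study, we defined abnormal CSF as WBCs >5/ul". The reason given there is that people without HIV were included and that "our PLWH were largely on antiretrovirals with suppressed plasma HIV RNA, we were unlikely to overdiagnose neurosyphilis".

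Three other statements bear on the point:

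- Procedures makes lumbar puncture conditional ("lumbar puncture, when indicated"). It also says that provider and participant "decided whether neurosyphilis treatment was indicated based on CSF abnormalities alone", without saying which abnormalities.
- The opening section on enrolment explains the symptom restriction on nonrandomized participants as "based on our previous observation that these symptoms predicted a reactive CSF-VDRL".
- Data analysis gives the entry model: "Odds ratios (ORs) with 95% CI for categories of cognitive impairment at study entry were determined by univariate or multivariate ordinal logistic regression". It lists no covariates and does not say where CSF status enters.

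**The concern.** The study collected two CSF markers and uses one. The stated reason deals with false positives, meaning a raised cell count due to HIV rather than syphilis. It does not deal with the opposite error, a reactive CSF-VDRL at a low cell count. The enrolment section itself treats CSF-VDRL as informative, so its absence from the definition stands out. Someone could also have been treated for neurosyphilis on CSF-VDRL and then be analysed as having normal CSF.

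At stake is any odds or hazard ratio by CSF status. If discordant participants share the cognitive risk of the high-cell group, placing them in the reference group pulls the ratio toward 1. With at most 96 participants, and CSF from only some of them, moving a few people might carry a result across 0.05. The reason given also depends on viral suppression being general rather than universal, so some pleocytosis from HIV could remain in the abnormal group.

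**Working it through.** The plan ties no sample size, power or event target to the CSF definition, so there is no figure of its own to reproduce. What follows is an illustration.

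**Inputs.** From the documents: the definition, the three entry categories (none, mild, moderate or severe combined) and the entry set of 96, which is an upper limit on the number with CSF. Assumed:

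- reference distribution 70/20/10%
- common odds ratio 3.5
- 30% of CSF samples with more than 5 cells/ul
- 40 to 96 participants with CSF
- a share *f* of the low-cell group with reactive CSF-VDRL, *f* = 0, 2, 5 or 10%

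**Raised-risk distribution.** Multiply the cumulative odds by 3.5.

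- Any impairment: 0.30/0.70 × 3.5 = 1.50, so 0.60.
- Moderate or severe: 0.10/0.90 × 3.5 = 0.389, so 0.28.
- The group is therefore 40/32/28%.

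**Case A: discordant participants carry the raised risk.** Under the cell-count definition the reference group is the mixture *f* × raised + (1 − *f*) × reference. At *f* = 10% that is 67.0/21.2/11.8%. The combined definition (high cell count or reactive CSF-VDRL) is undiluted.

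**Case B: discordant participants carry the reference risk.** The cell-count definition is undiluted. The combined abnormal group mixes 0.30 raised with 0.70*f* reference. At *f* = 10% that is 0.30 and 0.07, or 45.7/29.7/24.6%.

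Large-sample maximum-likelihood proportional-odds fits give:

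| *f* | A: cell count only | A: combined | B: cell count only | B: combined |
|---|---|---|---|---|
| 0 | 3.50 | 3.50 | 3.50 | 3.50 |
| 2% | 3.39 | 3.50 | 3.50 | 3.33 |
| 5% | 3.24 | 3.50 | 3.50 | 3.10 |
| 10% | 3.00 | 3.50 | 3.50 | 2.81 |

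The two cases mirror each other. Neither definition is the safer one without knowing the risk of the discordant participants.

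**False positives.** If 5, 10 or 20% of the high-cell group had HIV-related pleocytosis at reference risk, the cell-count odds ratio would be 3.30, 3.12 or 2.78.

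**People involved.** The number is *N* × 0.70 × *f*. For *N* = 40 to 96:

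- *f* = 2%: 0.6 to 1.3
- *f* = 5%: 1.4 to 3.4
- *f* = 10%: 2.8 to 6.7

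**Against sampling error.** The same model gives these standard errors of the log odds ratio, with 95% limits 3.5 × exp(±1.96 SE). The shift in the last column is ln(3.50/3.00) = 0.154 divided by the SE.

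| *N* with CSF | SE | 95% limits | Shift to 3.00, in SE |
|---|---|---|---|
| 40 | 0.680 | 0.9 to 13.3 | 0.23 |
| 80 | 0.481 | 1.4 to 9.0 | 0.32 |
| 96 | 0.439 | 1.5 to 8.3 | 0.35 |

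At *f* = 5% the shift is ln(3.50/3.24) = 0.077, or 0.11 to 0.18 SE.

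**Binary check.** Take 40% impaired in the reference group and odds ratio 3, so the raised-risk odds are 0.667 × 3 = 2, a risk of 0.667. Under case A at *f* = 10% the reference risk is 0.9 × 0.40 + 0.1 × 0.667 = 0.427, with odds 0.744, and the observed odds ratio is 2/0.744 = 2.69. At 2% and 5% it is 2.93 and 2.84. With all 96 having CSF and 30% above 5 cells/ul, two-sided power at 0.05 falls from 0.68 to 0.66, 0.63 and 0.58.

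**The two CSF phrases.** Procedures describes what provider and participant went by in deciding on treatment, and adds that they did not know the cognitive results. Data analysis sets a variable for the analysts. They serve different purposes and neither contradicts the other.

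**The case for a change.** The best case for a change is that the check is cheap and the gap is real. Both markers and HIV RNA are already recorded. One cross-tabulation would show whether discordant participants exist, and a recode would show whether conclusions depend on the definition. The stated reason defends specificity only. Under case A at 10% the binary illustration loses about 10 points of power (0.68 to 0.58), which is not trivial in a study this small.

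Part of this stands. The reason is one-sided, the handling of discordant results is not written down, and a result close to 0.05 could turn on a few people. Three things weaken the rest.

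- The 10% figure is an assumption, and the documents point to something lower. Nonrandomized participants were screened on symptoms linked to a reactive CSF-VDRL, and the original randomized plan took people who did not meet the symptom criteria for lumbar puncture.
- Two estimates with intervals as wide as 1.4 to 9.0 would rarely show which of cases A and B applies.
- Enrolment ended in March 2018, so repeating every analysis under a second definition, and again in a virally suppressed subset, would add post hoc tests at 0.05, each on fewer or reshuffled participants. The subset would be the least precise, and it addresses the one risk for which the authors gave a reason.

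**Conclusion.** The description is accurate: discordant participants fall outside the definition, and no sensitivity analysis is stated. It does not show an error. The analysts chose one explicit rule, gave a reason, and can apply it without ambiguity. The alternative is not shown to be better, since it dilutes the odds ratio as readily (2.81 against 3.50 at 10% under case B) as the cell count does (3.00 against 3.50 under case A).

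In the ordinal illustration the cell-count shift is 0.23 to 0.35 of a standard error at 10% discordance, 0.11 to 0.18 at 5%, and zero if nobody is discordant. This rests on the assumed distribution, odds ratio, prevalence of pleocytosis and number of lumbar punctures, and on CSF status entering the models at all, which the plan does not state.

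Reporting the cell count against CSF-VDRL would be good practice. If discordant participants turn up, one repeat of the main CSF analysis under the combined definition, labelled post hoc, would be reasonable. Both are optional reporting and leave the plan as it is.
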